#### False positive:

- 1) For patients undergoing systemic treatment (alone or in combination with targeted treatment): If on post-treatment follow-up imaging within 3-12 months, lymph nodes seen on CT or MRI increase by more than 20% in short axis diameter and PSA decreases by more than 50%.
- 2) In subjects with localized suspected lymph node(s) receiving targeted treatment without concomitant systemic treatment there are two ways to meet false positive disease:
  - If the subject does not demonstrate a decrease of PSA by greater than 50% after targeted treatment [OR]
  - If on post-treatment follow-up imaging within 3-12 months, lymph nodes seen on CT or MRI increase by more than 20% in short axis diameter (with a minimum of 3 mm in change in size)
- 3) For untreated patients: If on follow-up imaging within 3-12 months, lymph nodes seen on CT or MRI decrease by more than 30% in short axis diameter (with a minimum of 3 mm in change in size).

If all regions in a patient/region do not meet criteria for either True positive or False positive disease, then the patient/region will be considered unevaluable for primary endpoint.

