# 1 Clinical Protocol

# 1.1 IMPACT OF F-DCFPyL PET/CT ON INITIAL AND SUBSEQUENT TREATMENT STRATEGIES OF PATIENTS WITH PROSTATE CANCER (PROSPYL).

# 1.1.1 BACKGROUND AND RATIONALE

Prostate cancer is the most commonly diagnosed cancer and second leading cause of cancer death in American men (Edwards et al., 2014). Imaging and staging of prostate cancer is critical for treatment planning. Existing conventional imaging (CT, MRI and bone scans) has a low sensitivity in detecting local recurrence or metastatic disease. Choline based PET tracers are commonly used because of their affinity to prostate cancer but their diagnostic capability is limited, and they cannot reliably identify local recurrence, lymph node involvement, or soft-tissue deposits (Evangelista et al., 2013; Perera et al., 2016). Gallium-68 labeled HBED-CC PSMA (more commonly called Ga-PSMA-11) has been shown to be superior to choline based PET agents for the staging of prostate cancer, both Carbon11 and Fluorine-18 compounds (Afshar-Oromieh et al., 2014; Morigi et al., 2015; Schwenck et al., 2017). PSMA is expressed on the majority of prostate cancer cells, and is an ideal cell membrane protein to image. The detection rate of PSMA-11 for metastatic lesions in patients with recurrent prostate cancer is high: 50% for patients with a PSA less than 1 ng/ml, and above 85% for patients with a PSA greater than 2 ng/ml (Eiber et al., 2015; Perera et al., 2016). Several studies have reported a high impact on management of patients with biochemical recurrence after curative primary treatment with a rate of management change of 61%, 53%, 62%, 76% (Albisinni et al., 2017; Hope et al., 2017; Roach et al., 2017; Sterzing et al., 2016). In two studies, the impact on management was lower for initial staging indication: 26% and 21% (Roach et al., 2017; Sterzing et al., 2016). Limitations of Ga-PSMA-11 PET imaging include: a) rapid urinary excretion resulting in intense bladder accumulation obscuring the prostate region, 2) the requirement of local radionuclide generators for labeling 3) shorter half-life and reduced spatial resolution as compared to F agents. Recently developed second-generation PSMA PET probes using an F label, for example F-DCFPyL, overcome these limitations of Ga-based tracers. Preliminary studies have shown that F-DCFPyL to be promising for evaluation of metastatic prostate cancer. Therefore, we intend to perform a separate analysis of initial versus subsequent management as management options are considerably different (curative versus salvage/palliative).

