#### True positive:

1) For patients undergoing systemic treatment (alone or in combination with targeted treatment): If on post-treatment follow-up imaging within 3-12 months, lymph nodes seen

on CT or MRI decrease by more than 30% in short axis diameter and PSA declines by more than 50%.

- If PSA increases by more than 50% on systemic therapy, then a increase in the size of lesion by more than 20% will be considered a true positive lesion.
- 2) In subjects with localized suspected lymph node(s) receiving targeted treatment without concomitant systemic treatment there are two ways to meet true positive disease:
  - If the subject shows a decrease of PSA by greater than 50% after targeted treatment and the lymph node does not enlarge (change in size less than 20% or less than 3 mm increase in short axis diameter) [OR]
  - If on post-treatment follow-up imaging within 3-12 months, lymph nodes seen on CT or MRI decrease by more than 30% in short axis diameter (with a minimum of 3 mm in change in size)
- 3) For untreated patients: If on follow-up imaging within 3-12 months, lymph nodes seen on CT or MRI increase by more than 20% in short axis diameter (with a minimum of 3 mm in change in size).

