#### True positive:

- 1) If there was a corresponding positive sclerotic lesion on the CT portion of the  $^{68}$ Ga- $^{18}$ F-DCFPyL PET or on a separate CT obtained  $\leq$  30 days before or after the PET/CT in the same location as the PSMA uptake.
- 2) If there is focal uptake seen in the same location as the PSMA uptake on the baseline bone scan performed within one month of F-DCFPyL PET.
- 3) If there is a lesion noted in the same location as the PSMA uptake on the initial MRI performed within one month of F-DCFPyL.

- 4) If within 12 months follow-up CT demonstrates development of sclerosis in the same location as the PSMA uptake.
- 5) If within 12 months follow-up MRI demonstrates a new bone lesion in the same location as the PSMA uptake.
- 6) If within 12 months follow-up bone scan demonstrates new focal uptake in the same location as the PSMA uptake.
- 7) In subjects with localized suspected bone lesion(s) receiving targeted treatment without concomitant systemic treatment:
  - If the subject demonstrates a decrease of PSA by greater than 50% after targeted treatment.

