# False positive:

- 1) In subjects with localized suspected bone lesion(s) receiving targeted treatment without concomitant systemic treatment:
  - If the subject does not demonstrate a decrease of PSA by greater than 50% after targeted treatment with curative intent (ie non-palliative radiation).
- 2) If F-DCFPyL positive bone lesions do not meet the criteria for true positive findings, and appropriate correlative and follow-up imaging was acquired.

If bone lesions do not meet criteria for either true positive or false positive disease listed above, then the patient/region will be considered unevaluable for primary endpoint.

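### After targeted-only treatment, absence of a >50% PSA fall makes a node, visceral or prostate lesion false positive whatever the treatment intent, but for bone only after curative-intent treatment; this can bias PPV downward in regions 1-3

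*Combined protocol and SAP*

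**What the plan says.** The follow-up reference standard is in section 1.1.8.4, under 2) Secondary Outcome Measurement, A) Follow-up imaging. Each lesion type has its own true-positive and false-positive rules.

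- **Nodes, false positive 2).** The scope is set by "In subjects with localized suspected lymph node(s) receiving targeted treatment without concomitant systemic treatment there are two ways to meet false positive disease". The first way is "If the subject does not demonstrate a decrease of PSA by greater than 50% after targeted treatment [OR", and the second is growth of more than 20% and at least 3 mm. Treatment intent is not mentioned.
- **Visceral and prostate/prostate bed, false positive 2).** The PSA bullet is worded identically, again without mention of intent.
- **Bone, false positive 1).** The preamble about localized suspected disease and targeted-only treatment is the same, but the criterion reads "If the subject does not demonstrate a decrease of PSA by greater than 50% after targeted treatment with curative intent (ie non-palliative radiation".
- **Bone, false positive 2).** A second route has no counterpart for the other lesion types. It applies if "positive bone lesions do not meet the criteria for true positive findings, and appropriate correlative and follow-up imaging was acquired".

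The matching PSA true-positive criteria carry no intent condition for any lesion type. For bone (rule 7) the text is "If the subject demonstrates a decrease of PSA by greater than 50% after targeted treatment". For nodes the PSA fall must also come without enlargement.

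Part C of the same section ranks pathology above follow-up. It counts false-positive regions in the analysis and leaves unevaluable regions out. PPV per patient and per region, separately for initial staging and restaging, is a secondary endpoint (1.1.3.3).

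**The concern.** The same criterion is written in two ways. The bone wording accepts that a missing PSA fall refutes a lesion only when treatment was meant to eradicate the disease. The other three lesion types treat a missing fall as refutation in every case. By Table 1, nodes belong to regions 2 and 3, visceral lesions to region 3, and prostate and prostate bed to region 1. The unrestricted wording therefore governs three of the four regions.

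If a real node, visceral deposit or prostate lesion is treated palliatively and PSA does not fall by more than half, the rule records a PET error where there was none. PPV is reported by region, so part of a low value in regions 1-3 could come from the wording of the reference standard and not from the tracer.

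**Working it through.** The plan states no expected PPV and no count of palliatively treated lesions, so there is no figure to reproduce. The check has two parts.

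**1. Apply the written rules.** Take targeted treatment without systemic treatment and no PSA fall above 50%.

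| Size change on follow-up | Nodes, visceral, prostate | Same lesion types if the bone condition applied and intent was palliative |
|---|---|---|
| Shrinks >30% and at least 3 mm | Meets true positive and false positive | True positive only |
| Stable | False positive only | Neither, so unevaluable |
| Grows >20% and at least 3 mm | False positive (PSA and size) | False positive (size) |

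- Shrinking row: the node true-positive route is "lymph nodes seen on CT or MRI decrease by more than 30% in short axis diameter (with a minimum of 3 mm in change in" [...]. It holds whatever PSA does. Part C, region level, puts true positive above false positive when both rest on follow-up, so this lesion should not lower regional PPV.
- Growing row: the separate size bullet already gives false positive, so the intent condition changes nothing.
- Stable row: this is where the two wordings part. The lesion enters the PPV denominator as false positive under one wording and drops out under the other.

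At patient level, part C 1) c) ii) makes the patient false positive if there is no pathology, no region is true positive and one region is false positive. A stable lesion that is the patient's only classified finding therefore lowers per-patient PPV too.

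**2. Illustrate the size.** PPV = TP / (TP + FP). All counts are assumptions.

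Assume 60 otherwise verified nodal regions with 54 true positives: 54/60 = 90.0%. Add k real, stable, palliatively treated lesions as false positives:

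- k = 3: 54/63 = 85.7%
- k = 6: 54/66 = 81.8%
- k = 9: 54/69 = 78.3%

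Under the bone condition these k lesions would be unevaluable and PPV would stay at 54/60 = 90.0%. If their true status were known, it would be 57/63 = 90.5%, 60/66 = 90.9% or 63/69 = 91.3%.

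A second illustration takes 100 PET-positive regions with a true PPV of 90%, of which x are affected real lesions. Current wording gives (90 - x)/100 and the bone condition gives (90 - x)/(100 - x). Intervals are Wilson 95%, the method named in 1.1.9.5.

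| x | Current wording | Bone condition |
|---|---|---|
| 2 | 88/100 = 88.0% (80.2-93.0) | 88/98 = 89.8% (82.2-94.4) |
| 5 | 85/100 = 85.0% (76.7-90.7) | 85/95 = 89.5% (81.7-94.2) |
| 10 | 80/100 = 80.0% (71.1-86.7) | 80/90 = 88.9% (80.7-93.9) |

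Over x = 1 to 10 and true PPV from 80% to 95%, the current wording loses x points, that is 1 to 10. The bone condition loses about 0.1 to 2.2 points, because dropping real lesions from both counts still lowers PPV slightly.

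**The case against.** **The preamble may already imply curative treatment.** One could say that localized suspected disease given targeted treatment alone is treated to cure. This does not stand: the bone rule has the same preamble and still adds "after targeted treatment with curative intent (ie non-palliative radiation", so the protocol treats these as separate conditions.

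**The affected group is narrow.** This stands. The lesion must be treated without systemic therapy and with palliative intent, must not shrink enough to be true positive, must lack deciding pathology, and must share its region with no true-positive lesion. Part C also lets investigators depart from the criteria in individual patients, with recording. That discretion narrows the gap but is not a prespecified rule, and it can be used differently from case to case.

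**The size is hypothetical.** This stands too. No count in the documents supports 3 to 9 lesions per 60, and zero is not excluded. The Wilson interval for 54/60 is 79.9-95.3%, so 85.7% and 81.8% lie inside it and only 78.3% lies outside. Section 1.1.9.5 plans PPV with confidence intervals and no test between regions.

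**Two stronger readings are tempting.** A reader might infer that the bone wording pushes bone PPV up, because a PSA fall confirms a palliatively treated bone lesion while a missing fall does not refute it. The documents do not support this. Bone false positive 2) still refutes a lesion that meets no true-positive criterion once imaging was acquired, and follow-up imaging is planned for all patients. Nor do the documents show that a PSA fall above 50% after palliative treatment is weak confirmation.

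A reader might also infer that the effect falls mainly in restaging, because section 1.1.1 says that "management options are considerably different (curative versus salvage/palliative" between the initial and subsequent settings. That phrase describes management in general. It does not show how often localized non-bone lesions receive palliative targeted treatment alone.

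**Conclusion.** The inconsistency is real and is unexplained in the text. For nodes, visceral lesions and prostate or prostate bed, a real, stable, unbiopsied lesion treated palliatively without a PSA fall above 50% is scored false positive. Under the bone condition it would be unevaluable. The direction is downward for PPV in regions 1-3, and for per-patient PPV where no other region is true positive.

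The size cannot be derived from the documents. The drop from 90.0% to between 85.7% and 78.3% rests wholly on the assumed 54/60 and on 3 to 9 affected lesions. No claim is made about bone PPV or about a difference between initial staging and restaging. The primary management-change endpoint is untouched. The point is worth correcting because the correction is small and can be made before lesions are classified, but it is not a threat to the trial's main conclusion.

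**What to change.** - Reconcile the PSA bullet of false positive 2) for nodes, visceral lesions and prostate lesions with the curative-intent condition in bone false positive 1). If the bone-only limit is deliberate, say so and give the reason.
- Record treatment intent for each lesion given targeted treatment.
- State that non-bone lesions treated without curative intent are classified by pathology or by the existing size and true-positive criteria, and are otherwise unevaluable.
- Leave the PSA true-positive criteria unchanged for all lesion types. Limiting bone true positive 7) to curative intent could do harm. A palliatively treated bone lesion with a PSA fall, imaging acquired and no other true-positive criterion would move from true positive to false positive under bone false positive 2).

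The cost is an edit to three bullets, one added data item and a few more unevaluable lesions. Reporting the number of lesions made unevaluable in this way would show how much the condition matters. The change concerns how outcomes are classified and implies nothing about how patients should be treated.

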#### False positive

- For patients undergoing systemic treatment (alone or in combination with targeted treatment): If on post-treatment follow-up imaging within 3-12 months, lesions seen on CT or MRI increase by more than 20% in long axis diameter and PSA decreases by more than 50%.
- 2) In subjects with localized suspected lesions(s) receiving targeted treatment without concomitant systemic treatment there are two ways to meet false positive disease:
  - If the subject does not demonstrate a decrease of PSA by greater than 50% after targeted treatment [OR]
  - If on post-treatment follow-up imaging within 3-12 months, lesions seen on CT or MRI increase by more than 20% in long axis diameter (with a minimum of 3 mm in change in size).
- 3) For untreated patients: If on follow-up imaging within 3-12 months, lesions seen on CT or MRI decrease by more than 30% in long axis diameter (with a minimum of 3 mm in change in size).

If all regions in a patient/region do not meet criteria for either True positive or False positive disease, then the patient/region will be considered unevaluable for primary endpoint.

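### After targeted treatment alone, a lesion that grows >20% (at least 3 mm) while PSA rises >50% counts against PPV as a false positive, although the same record is true positive if untreated and, for nodes and visceral lesions, on systemic treatment

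*Combined protocol and SAP*

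**What the plan says.** The rules are in section 1.1.8.4, 2) Secondary Outcome Measurement, A) Follow-up imaging, set out by lesion type and by treatment received.

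**Nodes, targeted treatment without systemic treatment.**
- False positive rule 2 has two limbs joined by OR. The PSA limb reads: "If the subject does not demonstrate a decrease of PSA by greater than 50% after targeted treatment [OR". The size limb applies to nodes that "increase by more than 20% in short axis diameter (with a minimum of 3 mm in change in size", whatever PSA does.
- True positive rule 2 also has two limbs. One reads "If the subject shows a decrease of PSA by greater than 50% after targeted treatment and the lymph node does not enlarge". The other needs shrinkage of more than 30% and at least 3 mm.

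**Nodes, untreated.** True positive rule 3 begins: "For untreated patients: If on follow-up imaging within 3-12 months, lymph nodes seen on CT or MRI increase by more than 20". The figure is a percentage of the short axis, and a 3 mm minimum applies. PSA plays no part.

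**Nodes, systemic treatment.** A branch under true positive rule 1 covers patients whose PSA has risen by over 50% while on treatment: "then a increase in the size of lesion by more than 20% will be considered a true positive lesion". It has no 3 mm minimum.

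**Visceral lesions** repeat all of this in long axis; the size limb of false positive rule 2 is "lesions seen on CT or MRI increase by more than 20% in long axis diameter (with a minimum of 3 mm in change in size". **Prostate lesions** have the same targeted-treatment false positive rule and the same untreated true positive rule, but no PSA-rise branch under systemic treatment. **Bone** has a different targeted-treatment false positive rule, based on PSA and limited to treatment given for cure, and is not part of this point.

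Part C) of the same section ranks pathology above follow-up, calls the criteria a guide and lets investigators depart from them in individual patients, with a record kept. Section 1.1.9.5 reports PPV per patient and per region with Wilson 95% intervals.

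**The concern.** One set of follow-up findings leads to opposite verdicts on whether the PET finding was cancer, and only the treatment differs. In an untreated patient growth counts as evidence of cancer. On systemic treatment, growth with a PSA rise above 50% does too. After targeted treatment alone, the same growth and PSA rise count as evidence against cancer. No section gives a reason for the reversal or treats failure of targeted treatment as an outcome of its own.

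At stake is PPV, secondary endpoint 2 in section 1.1.3.3, which is to be assessed separately for initial staging and restaging. For this pattern the error runs one way: a real lesion that progresses leaves the numerator and stays in the denominator. Agreement between the three blinded readers would not reveal it, because the follow-up rules are the same for all of them.

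**Working it through.** **Step 1: one record through the rules.** Take a PET-positive lesion that grows from 10 to 14 mm (+4 mm, 4/10 = +40%) while PSA rises by 60%, with no pathology.

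| Lesion | Untreated | Systemic treatment | Targeted treatment only |
|---|---|---|---|
| Node | true positive (rule 3) | true positive (PSA-rise branch) | false positive, both limbs of rule 2 |
| Visceral | true positive (rule 3) | true positive (PSA-rise branch) | false positive, both limbs of rule 2 |
| Prostate or bed | true positive (rule 3) | neither, so unevaluable | false positive, both limbs of rule 2 |

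In the last column no true positive limb can be met, because each needs either a PSA fall above 50% or shrinkage above 30%. This is therefore not an overlap that a tie-break would settle.

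**Step 2: how far the conflict reaches (nodes, same growth).**
- PSA +30%: untreated true positive, systemic unevaluable, targeted only false positive.
- PSA -60%: untreated true positive, systemic false positive, targeted only false positive.

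The conflict with the systemic rule therefore needs a PSA rise above 50%. The conflict with the untreated rule does not depend on PSA.

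**Step 3: effect on reported PPV.** The plan states no expected PPV, so there is no figure to reproduce. All inputs are assumptions:
- P = true PPV = 90%
- s = share of truly positive evaluable patients given targeted treatment alone = 10-40%
- f = share of those who fail with this pattern and are not rescued by another provision = 5-15%
- every other real lesion is scored true positive

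Reported PPV = P × (1 − s × f), so loss = P × s × f.
- Low end: 0.90 × 0.10 × 0.05 = 0.0045, a loss of about 0.5 points (90% to 89.55%).
- High end: 0.90 × 0.40 × 0.15 = 0.054, a loss of 5.4 points (90% to 84.6%).

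With an assumed 100 evaluable PET-positive patients, the Wilson interval is 82.6% to 94.5% around 90%, and 76.3% to 90.4% around 84.6%.

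**Step 4: the two possible corrections at the high end.** Per 100 patients, 90 × 0.40 × 0.15 = 5.4 are affected. Scored true positive, PPV returns to 90%. Scored unevaluable, they leave numerator and denominator: 84.6/(100 − 5.4) = 84.6/94.6 = 89.4%.

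**The case against.** The PSA limb looks deliberate. Failure of PSA to fall after targeted treatment counts as false positive for nodes, visceral, prostate and (with the restriction to treatment for cure) bone lesions. The reasoning may be that if treating the lesion does not lower PSA, the lesion was not the source. That is a fair defence of the PSA limb for a lesion that stays stable. It does not explain the size limb, nor why growth with rising PSA points to cancer in the other groups and away from it here. If growth might be a treatment effect, that argues for unevaluable, not false positive.

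Other provisions soften the effect. Pathology prevails where it exists, though it is sought only when feasible. Per patient, one true positive region is enough even if another region is false positive on follow-up. Per region, a true positive lesion in that region outweighs a false positive one on follow-up. Investigators may deviate. These points stand and limit the number of affected patients. None is a rule for treatment failure, and none helps when the treated lesion is the only one and has no pathology.

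A reader might also infer more than the documents support:
- **A loss of 4 to 13.5 points.** This follows from P × f with true PPV 80-90% and f = 5-15% (0.80 × 0.05 = 4; 0.90 × 0.15 = 13.5), but only within a targeted-treatment-only stratum, which the plan does not report.
- **A conflict with the systemic rule at any PSA rise, or for prostate lesions.** Step 2 and the table show otherwise.
- **Unequal bias between initial staging and restaging.** This depends on the treatment mix, which the documents do not give.

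**Conclusion.** The inconsistency is real and follows from the text alone. For nodes, visceral and prostate lesions after targeted treatment without systemic treatment, growth above 20% and at least 3 mm with a PSA rise above 50% is scored false positive. The untreated rules call it true positive for all three lesion types; the systemic rules do so for nodes and visceral lesions only. For real lesions of this type the effect on PPV is downward, subject to the overrides named above.

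The size cannot be derived from the documents. Under the assumptions in step 3, overall PPV falls by about 0.5 to 5.4 points.

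The consequence is limited to a secondary endpoint with no stated success threshold. The closing sentences of these rules speak of lesions being unevaluable for the primary endpoint, so a reader might infer that the primary result is affected. Section 1.1.3.3 makes management change the primary endpoint, and neither it nor the sample size of 400 depends on these rules. The point should be corrected, but it does not threaten the trial's main conclusion.

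**What to change.** Before PPV is analysed, reconcile the targeted-treatment rules for nodes, visceral and prostate lesions with the untreated and systemic rules. State that growth above 20% (at least 3 mm) with a PSA rise above 50% after targeted treatment alone is not false positive, and that this takes precedence over false positive rule 2. Two scorings are defensible:

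- **True positive**, in line with the systemic branch for nodes and visceral lesions. The 3 mm minimum would be an addition to that branch, and the branch itself would be new for prostate lesions. Its cost is that a benign lesion that grows while PSA rises from disease elsewhere would count as true positive, a risk the systemic rule already accepts.
- **Unevaluable**, which avoids that risk but drops the lesion from PPV.

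Either is a short text change and needs no new data. Neither touches lesions that grow with a smaller PSA rise, or that stay stable without a PSA fall above 50%. Those remain false positive under rule 2, and the sponsor should confirm that this is intended.
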